## **1. BACKGROUND AND RATIONALE**

Mepolizumab is a humanized monoclonal antibody (IgG1, kappa) against IL-5, which mediates the role of the eosinophils in the inflammatory process of the airways. The drug has a high affinity to IL-5 and blocks the binding of IL 5 to the alpha chain of the IL-5 receptor complex expressed on the eosinophil cell surface. At present, mepolizumab is registered in the European Union as an adjunctive therapy in adults and paediatric patients aged 6-17 years with inadequately controlled severe eosinophilic asthma. In Poland mepolizumab has been a reimbursable drug since 1st November, 2017 and is available under the national drug program for adults with severe eosinophilic asthma.

The published results of the clinical trials show that the use of mepolizumab in the treatment of patients with severe eosinophilic asthma reduces the exacerbation rates, as well as decreases the doses of glucocorticosteroids (with the maintenance of asthma control). Moreover, mepolizumab demonstrates: long-term reduction of eosinophilic inflammation, consistent and sustained exacerbation reductions and improvements in asthma control for the duration up to 4.5 years.

The proposed real-life observation study can deliver valuable information about mepolizumab efficacy complementing the results of clinical trials. Multicentre design of the study will allow to collect data from relatively large group of patients treated at least one year within the Polish Drug programme. The added value of this retrospective study relies in the specifics of the Polish drug programme which has unique inclusion criteria with respect to the number of eosinophil cells in blood. (the unique inclusion criteria in the Polish drug programme is  $\geq 350$  eos/ $\mu$ l) Therefore we can test the efficacy of mepolizumab in the specific treatment group. To this time no study has been published about the efficacy of mepolizumab in Poland.

## **2. OBJECTIVES**

To evaluate the efficacy of mepolizumab 100 mg SC every 4 weeks in patients with severe eosinophilic asthma who have been treated for at least 12 months in several Polish allergy/asthma centres under the same protocol .

## **3. RESEARCH METHODOLOGY**

### **3.1. Study Design**

Retrospective multicentre observational study will involve 130 patients with severe eosinophilic asthma ( SEA ) who have been treated in six Severe Asthma Treatment Centres ( SATCs) in Poland.

In each SATC all data available in the program questionnaires will be transferred to the Study Data Sheet (questionnaire), and will be send to the study coordinator within 5 months from the study beginning

The start-up meeting including partners from all centres involved will be organized to discuss the study protocol and to unify data collection

The evaluation parameters (exacerbations rate, OCS dose) will be analysed at least at three time points: pre-MEPO, after 24 weeks of MEPO and after 1 year of MEPO administration (some of the outcomes will be observed every 4 weeks, for the details see 'study endpoints' section).

In addition the following parameters which are available in patients' records will be analysed:

- ACQ-5 score (measured at qualification for the treatment and every 4 weeks thereafter)
- AQLQ score (measured at qualification for the treatment and every 4 weeks thereafter)
- Pre-bronchodilator FEV1 (measured at qualification for the treatment and every 4 weeks thereafter)

Research activities will include:

- collecting raw data from the clinical centres (paper version) and constructing a raw dataset (digital version),
- data cleaning, computation of variables,
- statistical analysis typical for pre-post study design (the statistical analysis will be outsourced to the specialized private institute).

Clinical improvements observed at 24 weeks and at 52 weeks of treatment with Mepolizumab will be referred to the following characteristics of patients at baseline:

- demographics,
- presence of comorbidities including the atopic status,
- concomitant pharmacotherapy,
- clinical status,
- eosinophilia.

We will control for mepolizumab use regarding dose, treatment duration and dosing frequency as well as for the safety profile based on the AEs reporting in the medical documentation.

### **3.2. Data Source / Data Collection**

Patients recruited to the study had been treated with mepolizumab between December 2017 and December 2019.

All the data planned to be used in the proposed study were systematically collected in the form of the clinical documentation (paper version) and will be transferred in the study centres into the study Data Sheets.

Collaborating Researchers (Severe Asthma Centres' Leaders) will provide the data input into the dedicated online questionnaire.

### **3.3. Study Population**

130 Patients who were treated with mepolizumab in six severe-asthma clinics in Poland between December 2017 and December 2019. In the drug program in Poland it was mandatory to conduct the control examinations at the 24th and 52nd week of the treatment. In the proposed study we will use this information to evaluate study endpoints. Only patients who have been treated for at least 52 weeks are included into the study

#### **3.3.1. Inclusion Criteria**

- The availability of the complete data

- Duration of treatment with mepolizumab:  $\geq 52$  weeks
- Satisfying the Polish drug programme inclusion criteria:
  - Age  $>18$
  - Before treatment with mepolizumab (BSAT inclusion criteria):
    - High doses of ICS + one other controlling medication (i.e. LABA)
    - $\geq 2$  exacerbations in the previous year
    - $\geq 350$  eosinophil cells/ $\mu\text{l}$  in the blood at the time of qualifying, or in the previous year
    - Pre-bronchodilator FEV1  $< 80\%$

### **3.3.2. Exclusion Criteria**

- Duration of treatment with mepolizumab  $< 52$  weeks
- Lack of complete data

## **3.4. Variables**

The main outcome variables are listed as the primary or secondary endpoints. Asthma exacerbation is defined as in the Polish drug programme (see 3.4.1.1.).

### **Variables concerning the primary endpoints**

- Asthma exacerbations measured at qualification for the treatment (in the period of previous 52 weeks) and at the 24th and 52nd week of the treatment.
- Oral Corticosteroids use dose (documented at qualification for the treatment and at the 24th and 52nd week of the treatment)

### **Variables concerning the secondary endpoints**

- ACQ-5 score (measured at qualification for the treatment and every 4 weeks thereafter)
- AQLQ score (measured at qualification for the treatment and every 4 weeks thereafter)
- Pre-bronchodilator FEV1 (measured at qualification for the treatment and every 4 weeks thereafter)
- Blood eosinophil counts (measured at qualification for the treatment and at the 24th and 52nd week of the treatment)

## **3.4.1. Outcome Definitions**

### **3.4.1.1. Asthma Exacerbation**

Asthma exacerbations, defined according to the Polish drug programme, is *the worsening in asthma requiring (1) use of systemic corticosteroids or (2) increase in dose of OCS for more than 3 days in case of patients who are chronically treated with OCS*.

### **3.4.2. Exposure Definitions**

There are no exposure variables to be defined in this study.

## **3.5. Sample Size**

Retrospective multicentre observational study will involve 130 patients with SEA who have been treated in six severe asthma treatment centres in Poland. The sample includes all individuals who participated in the drug programme in Poland at least for 52 weeks between December 2017 and December 2019

The motivation to focus on this sample was the following:

- a relatively large sample of patients (N=130),
- the unique and complete dataset containing patients' characteristics and treatment results (all severe asthma centres participating in the drug programme are obliged to collect all the data we use in this study),
- the opportunity to study the treatment results under the unique inclusion criteria of the Polish drug programme ( $\geq 350$  eos/ul) (see 3.3.1).

## **4. DATA ANALYSIS CONSIDERATIONS**

- Exacerbations rates in 24th and 52nd week with comparison to rate of exacerbations during the pre-treatment year. Also the frequency of exacerbations in 6- and 12-month follow-up period will be described as patient count and percentage as categorical variable (0,1,2,3,4+ exacerbations).
- OCS median doses in 24th and 52nd week with comparison to the median dose at baseline
- ACQ-5, AQLQ, FEV1 measured on the monthly basis, the mean score at baseline will be compared with every post-treatment monthly score.
- Blood eosinophil geometric mean in 24th and 52nd week with comparison to the geometric mean at baseline

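### The exacerbation baseline is the same 52-week count that had to be 2 or more for entry, with no comparator; this selection biases the raw before-after contrast toward benefit, and the plan neither shows nor states it

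*Combined protocol and SAP*

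**What the plan says.** - **Entry rule.** Section 3.3.1 requires, before mepolizumab, 2 or more "exacerbations in the previous year".
- **Baseline.** The list of primary-endpoint variables in Section 3.4 gives "Asthma exacerbations measured at qualification for the treatment (in the period of previous 52 weeks"), and then at weeks 24 and 52 of treatment.
- **Contrast.** Section 4 compares the week-24 and week-52 rates "with comparison to rate of exacerbations during the pre-treatment year". It also plans a table of patients with 0, 1, 2, 3 or 4+ exacerbations, for the 6- and 12-month follow-up only.
- **Design.** Section 3.1 describes one treated cohort and "statistical analysis typical for pre-post study design". No comparison group is described.
- **Claim.** Section 1 says "Therefore we can test the efficacy of mepolizumab in the specific treatment group", and Section 2 states the aim as "To evaluate the efficacy of mepolizumab 100 mg SC every 4 weeks". Section 1 also presents the study as "complementing the results of clinical trials".
- **Limitations.** Section 5 has one line, which again says that real-life studies complement trials. It mentions neither selection on the baseline count nor the missing comparator.

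**The concern.** The entry criterion and the baseline of a primary endpoint are one number. Requiring a count of 2 or more keeps patients whose year was bad by chance and drops similar patients whose year was good by chance. The next year's count has no such floor, so on average it falls back toward each patient's usual rate. This is regression to the mean. Without a comparator, nothing in the design separates that fall from a drug effect.

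Two outputs are affected. The rate comparison contains a component that is not due to treatment. The follow-up category table will show patients with 0 or 1 exacerbations. A reader may credit all of them to treatment, although everyone had at least 2 at baseline by rule and some would drop to 0 or 1 anyway. Section 7 plans conference presentation and publication, so the unqualified figures would reach readers who may not connect the entry rule with the result.

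**Working it through.** **Figure to reproduce.** None. The plan states no exacerbation rate, dispersion, effect size or significance level, and the 130 patients are those available, not a calculated sample size.

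**Inputs from the documents.** Threshold of 2 (Section 3.3.1); 52-week baseline window (Section 3.4); 52-week follow-up (Sections 3.3 and 4); 130 patients (Section 3.5).

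**Assumptions.** Each patient has a stable yearly rate drawn from a gamma distribution with mean μ and variance kμ². Counts before and after are independent Poisson given that rate. There is no drug effect. k ranges from 0.3 to 1.2.

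**Formulas.** With a = 1/k and b = a/μ:

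- E[pre | pre ≥ 2] = (μ − P(1)) / (1 − P(0) − P(1)), with P negative binomial
- E[post | pre ≥ 2] = (a + E[pre | pre ≥ 2]) / (b + 1)
- Apparent reduction = 1 − E[post | pre ≥ 2] / E[pre | pre ≥ 2]

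**Worked case, μ = 2, k = 0.5.** Here a = 2, b = 1, P(0) = 0.25 and P(1) = 0.25. Expected pre count: (2 − 0.25)/0.50 = 3.50. Expected post count: (2 + 3.50)/2 = 2.75. Apparent reduction: 1 − 2.75/3.50 = 21.4%.

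The same steps at k = 0.5 give 4.33 to 3.80 (12.3%) for μ = 3, and 6.09 to 5.78 (5.1%) for μ = 5.

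**By the baseline mean the study will observe.** The quantity to be reported is the mean in the selected patients, so I solved for the μ that gives each observed mean, at k = 0.3, 0.5, 0.8 and 1.2. For the categories, the post count given pre = x is negative binomial with shape a + x and probability (b + 1)/(b + 2), averaged over the truncated pre distribution.

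| Observed baseline mean | Apparent rate reduction, no drug effect | Share with 0-1 in 52 weeks, no drug effect (baseline: 0% by rule) |
|---|---|---|
| 3 | 31-34% | 44-49% |
| 4 | 14-17% | 23-31% |
| 5 | 7-10% | 14-22% |
| 7 | 3-5% | 6-15% |

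As an example, take an observed mean of 4 and k = 0.5. The baseline split 2/3/4+ is 30/23/47%. The 52-week follow-up split 0/1/2/3/4+ is 9/16/18/16/40% (rounded) with no drug effect.

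**When the drug does work.** Simulation with k = 0.5, 130 patients, 200 replicates and stable rates compared the raw rate ratio with one from a model conditioning on a pre-treatment count of at least 2. Cells show the median ratio, with the SD of the log ratio in brackets.

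| True ratio | Underlying mean μ | Raw | Conditioned |
|---|---|---|---|
| 1.00 | 2 | 0.79 (0.068) | 1.01 (0.084) |
| 1.00 | 3 | 0.88 (0.058) | 1.00 (0.068) |
| 1.00 | 5 | 0.95 (0.054) | 1.01 (0.056) |
| 0.50 | 2 | 0.40 (0.079) | 0.51 (0.093) |
| 0.50 | 3 | 0.44 (0.077) | 0.50 (0.086) |
| 0.50 | 5 | 0.48 (0.068) | 0.50 (0.072) |

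In these runs a true halving is exaggerated, not manufactured. The conditioned model also has a limit. With no drug effect, μ = 2 and independent yearly rate multipliers of variance 0.4, it gives 0.81 (raw 0.67), so it under-corrects when rates vary by year.

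**The case against.** The strongest reply is that only one component has been derived, with everything else held fixed. A reader might infer that the reported contrast must overstate the benefit overall. The documents do not support that. OCS dose is the other primary endpoint and Section 1 expects glucocorticosteroid doses to fall, which could raise exacerbations on treatment. The baseline count is recorded once at qualification, while several other measures are taken every 4 weeks on treatment, so events before treatment may be captured less completely; this is an inference that the documents do not state. This objection stands: the selection pushes toward benefit, but the net direction is open.

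A reader might also infer that the whole effect is an artefact, or that a significance test would nearly always reject with no drug effect. Neither follows. The documents name no test, and at an observed baseline mean of 5 or more the rate bias is about 10% or less if rates are stable.

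Section 3.4.2, "There are no exposure variables to be defined in this study", might be read as ruling out a comparator. It does not say so; the design description in Section 3.1 is the proper basis.

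Part of the problem is visible already. The entry rule is explicit, the baseline rate is planned output, improvements will be related to baseline clinical status, and the study is placed as complementary to trials. An alert reader could gauge the bias. But none of this names the mechanism or its direction, and the category table has no baseline counterpart. The plan defines no responder, so the risk there is one of reading, not of a stated analysis.

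Finally, a truncated-count model is a heavy addition to a descriptive plan, and one pre-treatment count per patient cannot check its assumptions. That stands, and it limits the model to a supportive role.

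**Conclusion.** The concern holds as a selection bias toward benefit in the raw primary exacerbation contrast, undisclosed in the plan. The structure is certain from Sections 3.1, 3.3.1, 3.4 and 4.

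The size cannot be determined from the documents. The tabulated range, from about a third at an observed baseline mean of 3 to a few percent at 7, rests on assumed gamma-Poisson counts, stable personal rates and dispersion 0.3-1.2. It would be larger if patients tended to qualify in an unusually bad year. The restriction to patients treated for at least 52 weeks is a separate selection and is not in these figures.

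The raw contrast cannot by itself show efficacy, but the documents do not show that an observed reduction would be mostly or wholly spurious. The plan should be changed, because the repair is cheap and affects what the study can conclude.

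**What to change.** **Section 4.** Keep the raw comparison. Report the baseline mean, and put the baseline distribution (2, 3, 4+) beside the follow-up table, with a footnote that baseline is at least 2 by eligibility. The baseline column covers 52 weeks, so it is the counterpart of the 12-month column only.

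**Section 5.** Name regression to the mean from the entry criterion, and the lack of a comparator.

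**Sections 1 and 2, and the report.** Word the exacerbation result as a change from the pre-treatment year, not as a test of efficacy.

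**Supportive sensitivity analysis only.** Fit a paired gamma-Poisson model conditioning on a pre-treatment count of at least 2, with a log person-time offset. State that it assumes gamma frailty and stable rates, under-corrects if rates vary by year, and does not address the 52-week treatment restriction. It should not carry the conclusion.

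**Cost.** A few lines of text, one table column and one model, all on data already collected. The downside is a somewhat smaller and less precise estimate beside the raw one: in the simulation the SD of the log ratio rose by 4% (0.056/0.054) to 24% (0.084/0.068). The text and the baseline column are the core; the model could be left out without losing them.

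### The OCS primary endpoint is specified only as medians at separate visits, with no OCS analysis set and no within-patient summary, so the stated comparison may not show a real dose reduction.

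*Combined protocol and SAP*

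**What the plan says.** Section 3.4 lists as a primary-endpoint variable "Oral Corticosteroids use dose (documented at qualification for the treatment and at the 24th and 52nd week of the treatment". The only OCS-specific analysis is one line in section 4: the median dose at week 24 and at week 52, "with comparison to the median dose at baseline".

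Three other places bear on who enters that median:

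- **Entry (section 3.3.1).** The background treatment required is "High doses of ICS + one other controlling medication (i.e. LABA". OCS use is not required.
- **Exacerbation definition (section 3.4.1.1).** It has a separate limb for an "increase in dose of OCS for more than 3 days in case of patients who are chronically treated with OCS". Chronic users are thus treated as a special case within the study population.
- **Population (sections 3.3 and 3.5).** There are 130 patients, and "The sample includes all individuals who participated in the drug programme in Poland at least for 52 weeks". Complete data are an inclusion criterion ("The availability of the complete data") and their absence is an exclusion criterion ("Lack of complete data"). No population specific to the OCS endpoint is defined.

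On method, section 3.1 promises "statistical analysis typical for pre-post study design", to be done by an outside institute, and says that clinical improvements will be related to baseline characteristics. It defines no change variable, interval or test for OCS.

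**The concern.** Because OCS is not needed for entry, the 130 patients may be a mix of users and non-users. If non-users are counted at 0 mg, the median of the whole group depends first on how many patients use OCS and only then on what happens to their doses. Below half users it stays at 0 whatever the users do. Just above half, it can drop to 0 when very few patients stop. Comparing medians at separate visits also ignores that the same patients are measured each time.

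At stake is one of two primary-endpoint variables. A real reduction could be reported as no change, or two stoppers as a fall to 0 mg, depending on a user share that the plan does not give. The data already exist in clinical records, so if the set is not written down, it will be chosen by an analyst who can see the doses.

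**Working it through.** The plan gives no OCS figure to reproduce: no user count, dose distribution, expected reduction, alpha or power.

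**Inputs.** N = 130 (section 3.5). The number of users, u, is not stated and is varied. Non-users are set to 0 mg, and no non-user starts OCS later (both assumptions). Where mg figures appear, users' doses are assumed to cycle through 5, 5, 10, 10, 15 and 20 mg. The count thresholds need no dose assumption.

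**Step 1, the threshold.** With N = 130 the median is (x65 + x66)/2, where x65 and x66 are the 65th and 66th ordered doses. There are 130 − u zeros.

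- u = 64: 66 zeros, so x65 = x66 = 0 and the median is 0.
- u = 65: 65 zeros, so x65 = 0, x66 is the smallest positive dose, and the median is half that dose.

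The baseline median is therefore 0 exactly when u ≤ 64 (64/130 = 49.2%). A dose cannot go below 0, so it cannot fall further.

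**Step 2, every user halves the dose.** Halving every value halves the median, so any median above 0 follows.

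| Users of 130 | Median before | Median after |
|---|---|---|
| 39 to 64 (30-49%) | 0 | 0 |
| 78 (60%) | 5 mg | 2.5 mg |
| 91 (70%) | 5 mg | 2.5 mg |
| 104 (80%) | 10 mg | 5 mg |

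With 64 users the total is 10 × 65 + 30 = 680 mg. The mean falls from 680/130 = 5.23 to 2.62 mg while the median stays at 0.

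**Step 3, stoppers needed to bring the median to 0.** This is u − 64: 2 for 66 users, 4 for 68, 14 for 78, 27 for 91 and 40 for 104. With 66 users the total is 11 × 65 = 715 mg, the mean is 5.50 mg and the median is 5 mg. If two stop, the median is 0. The mean falls only to 705/130 = 5.42 mg (−1.4%) if both were on 5 mg, or to 675/130 = 5.19 mg (−5.6%) if both were on 20 mg.

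**Step 4, a paired change in all 130 is not enough.** With 64 users all halving, 66 of the 130 changes are 0, so the median paired change is also 0. The set has to be defined as well.

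**Step 5, a fixed group of baseline users.** Take 60 users: 20 on 5 mg, 20 on 10 mg, 10 on 15 mg and 10 on 20 mg. The median is 10 and the mean 650/60 = 10.83 mg.

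- All halve: median 10 to 5 mg.
- Only the 20 on 5 mg stop: median 10 to 10 mg, and the median paired change is 0. The proportion stopping shows it: 20/60 = 33%, Wilson 95% CI 23-46%.
- Those 20 stop and the 20 on 15-20 mg go to 10 mg: median 10 to 10 mg. Yet 40 of 60 reduced, the mean falls to 400/60 = 6.67 mg (−38.5%), and the median paired change is −5 mg.

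**The case against.** **A paired test may still see the change.** The generic pre-post wording in section 3.1 could be carried out as a Wilcoxon signed-rank test. Unchanged pairs drop out of that test, so it would detect change even with all 130 included. With 64 users all halving, the exact two-sided p is 2 × 2^−64 = 2^−63. With 20 stoppers and no other change it is 2 × 2^−20 = 2^−19, about 2 in a million. This stands as a limit on the point: the failure belongs to the medians set side by side, not to every analysis that the plan might allow. It does not close the gap, because the plan names no test and a p-value would not give the size of the reduction.

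**The zero median rests on unstated facts.** The documents do not say that all 130 enter, that non-users are coded 0 mg, or that 64 or fewer use OCS. The wording about OCS doses could equally mean doses among users, and a fixed group of users follows a general halving. This also stands. A reader might infer that the baseline median will be 0 and that the endpoint cannot show a reduction. The documents do not support that.

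**The last 60-user example is contrived.** It needs every patient outside the 10 mg dose to respond and fewer than half of those on it. If a tenth patient on 10 mg goes to 5 mg, the median moves to 7.5 mg. It shows that equal medians are possible in a users-only set, not that they are likely.

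**Conclusion.** The point holds in conditional form. What is certain is the omission: a primary-endpoint variable has no stated analysis set and no within-patient summary, in a population where OCS use is not required. What is conditional is the consequence. If all 130 enter with non-users at 0 mg, the medians are 0 and 0 for 64 or fewer users even when every dose is halved, and with 66 users two stoppers can take the median to 0. At about 60-80% users the median does follow a general halving. These counts are exact; the mg figures rest on assumed doses of 5-20 mg. It would be wrong to conclude that the endpoint fails, since the OCS share is unknown and a paired analysis, though not named, is not ruled out. This should be fixed before the analysis, with medium confidence that it would affect the reported result.

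**What to change.** In section 4:

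- Define the OCS analysis set as patients recorded as on chronic (maintenance) OCS at qualification, state their number, and keep those who stop at 0 mg.
- If the records cannot separate chronic use from a short course, use a recorded dose above 0 mg at qualification and say that the end of a short course may then be counted as a reduction. This matters here because entry requires at least two exacerbations in the previous year.
- Report the within-patient absolute and percentage change to weeks 24 and 52, with a confidence interval from a named paired method.
- Report the proportions who reduced and who stopped, with confidence intervals, because the median paired change can itself be 0 when a third of users stop. The medians may stay as description.

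**Cost.** This is mainly wording, since the doses at all three time points are already recorded. Identifying chronic use may need a check of the existing paper records. The set will be smaller than 130 if some patients are non-users, and intervals will be wider. For about one third stopping, the Wilson 95% CI is 21-49% with 39 users (13/39), 23-45% with 64 (21/64) and 25-43% with 104 (35/104).
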